## Scenario summary

research topic	Application of Single-Port Robot-Assisted Breast-Conserving Surgery via Axillary Approach for Breast Cancer.
Main purpose of the study	
1. To evaluate the efficacy of single-port robots in breast cancer breast conserving surgery. Including differences in operative time and intraoperative number of lymph nodes detected.
 
2. To evaluate surgical safety: the incidence of surgical transfer and the incidence of postoperative complications.

Secondary purpose of the study	Pain and cosmetic scores of patients after breast conserving surgery under a single port robotic approach.
research design	
 Randomized controlled trial
 
 non-randomized controlled study
 
 Single-arm study
 
 Other
 
 Single-center study    multicenter study
 
Whether blind:  yes  no

subject investigated	Patients undergoing breast-conserving surgery for breast cancer.
intervention study	Single-port Robot-assisted breast-conserving surgery for breast cancer.
endpoint criteria	Success rate of breast conservation surgery under single-port robotic approach
sample capacity	Total number of cases: 100; 20 in the test group; 80 in the control group

statistical analysis	Double data entry was carried out using Excel 2010, and data analysis was performed with SPSS 25.0. The normality of continuous variables and homogeneity of variance were examined by Kolmogorov-Smirnov test and analysis of variance test respectively. For continuous variables that conformed to normal distribution and had homogeneity of variance, the independent-samples t-test was adopted. For continuous variables that did not conform to normal distribution, the Mann Whitney U test was used. For categorical variables and count data, Fisher's exact test and Pearson chi square test were employed.
Study cycle	November 2024-December 2025

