shows that Jingfeng ®SP1000 is the first single-port surgical robot to enter the registered clinical trial in China. Jingfeng Medical ® has cooperated with top hospitals and top experts in China to carry out in-depth clinical research and trial of all departments of single-port surgical robot. At present, Jingfeng ®SP1000 has been approved for gynecological indications, and completed registered clinical trials in urology, general surgery, thoracic surgery and other fields, successfully carried out more than 200 clinical operations, demonstrating a wide range of adaptability and excellent performance, bringing new value to scientific research and clinical fields. In addition, professor [name]'s team[29-31]. For the first time, the domestic Jingfeng ®EDGE SP1000 surgical system was used to successfully simulate the key steps of thyroid surgery in the oral thyroid surgery simulator, and realized the high-definition vision and high stability of single-arm robot surgical system, and its smart arm technology, hidden sleeve function and zero pressure anchor point technology are more conducive to ensure the operation safety, this successful practice provides a solid foundation and rich experience for single-port robot breast surgery and related clinical research. However, the safety and effectiveness of the procedure have not been fully verified, and whether the single-port robotic transaxillary breast cancer surgery is more advantageous than the multi-channel operating system (Xi and Si) is not reported. Therefore, this study aims to fill this gap and compare the efficacy and safety of open breast cancer surgery and single-port robot in transaxillary breast cancer surgery through a prospective, single-center phase II clinical cohort study, so as to provide scientific basis for clinical practice and promote the development of minimally invasive breast cancer surgery technology. To provide a theoretical and practical basis for the future application of EDGE SP1000 surgical system in breast cancer surgery. In addition, on this basis, we will systematically establish the technical system and standard for single-port robot breast cancer surgery in our hospital, and lead the formulation of domestic single-port robot-assisted breast cancer surgery standard, which is this the clinical promotion and application of surgery to lay a solid foundation

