## 2. Purpose of Research

To evaluate the safety and feasibility of single-port robot in breast conserving surgery, and compare the advantages and disadvantages of single-port robot and traditional surgery in breast cancer complications, postoperative complications, perioperative recovery effect and safety of breast conserving surgery, so as to choose a more effective and safe surgical method.

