## 3. Research Design

### 3.1 Overall Study Design

-Enrollment: Subjects who meet the inclusion criteria enter the study process, including SPr-breast conserving surgery or Traditional-breast conserving surgery. The choice of the two surgical methods is based on the patients economic situation and the availability of equipment.

-Preoperative hospitalization: Collect patient disease information (including mammography, breast B ultrasound, breast enhanced MRI, etc.).

-The day of operation: Record the operation time, intraoperative bleeding volume, intraoperative complications, intraoperative adverse events, etc.

-Postoperative hospitalization: Record postoperative complications (postoperative bleeding, flap or nipple areola complex necrosis, subcutaneous emphysema, infection, capsular spasm, postoperative shoulder pain and discomfort, etc.), postoperative pain score, and postoperative pathological biopsy.

-Postoperative hospital stay: Calculated based on the number of days from surgery to discharge.

[figure not shown]
-28 days after surgery: To understand the complication rate and mortality rate within 28 days after surgery.

-90 days after surgery: To understand the complication rate and mortality rate within 90 days after surgery.

-Disease-free survival at 3 years after surgery (recurrence was defined as surgical area and distant metastasis by the time from surgery to last follow-up or date of recurrence and metastasis).

-3 year overall survival (from time from surgery to last follow-up or death).

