## 3.4 Study grouping and methods

### 3.4.1 Study groups and interventions

The surgical method is based on the advice of the physician, mainly on the own choice of patients and the availability of equipment. After rigorous preoperative evaluation, patients who met the inclusion criteria were prepared for preoperative preparation (including preoperative antibiotics, etc.). The observation group was the SPr-breast conserving surgery group and the control group was the tradition-breast conserving surgery group.

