#### 4.3 Preliminary analysis

Two-person data entry was performed using Excel 2010 and SPSS 25.0 data analysis. Baseline numerical data will be described as mean, standard deviation or median and interquartile range, and baseline categorical data will be shown as percentage. Normality and homogeneity of variance of continuous variables were tested by Kolmogorov-Smirnov test and ANA variance, respectively. Independent sample t-test for continuous variables meeting normal distribution and homogeneity of variance, Mann Whitney U test for continuous variables not meeting normal distribution, and Fishers exact test and Pearson chi square test for categorical variables and count data. Primary endpoint analysis: The success rate of breast conservation surgery under single hole robot will be compared by Chi-square test (Chi-square test) with exact test if necessary. Use multiple interpolation methods to deal with missing data. Postoperative cosmetic score and postoperative pain score were calculated and analyzed according to the standard scale.

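### Treatment is self-selected, yet every between-group comparison in SAP 4.3 is unadjusted and is meant to inform the choice of operation

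*SAP*

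**What the plan says.** The Scenario summary ticks the box "non-randomized controlled study" and marks the study as not blinded. Two sections describe how patients come to one operation or the other. Section 3.1 says: "The choice of the two surgical methods is based on the patients economic situation and the availability of equipment". Section 3.4.1 says: "The surgical method is based on the advice of the physician, mainly on the own choice of patients", and again adds equipment availability.

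Section 4.3 sets the analysis. For the primary endpoint: "The success rate of breast conservation surgery under single hole robot will be compared by Chi-square test", with an exact test if necessary. For continuous outcomes: "Independent sample t-test for continuous variables meeting normal distribution and homogeneity of variance", otherwise Mann-Whitney U. Categorical outcomes get Fisher's exact or Pearson's chi-square test. Baseline data have no role beyond description: "Baseline numerical data will be described as mean, standard deviation or median and interquartile range", and percentages for categorical items.

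The comparison has a stated use. Section 1 says the study is to "compare the efficacy and safety of open breast cancer surgery and single-port robot in transaxillary breast cancer surgery". Section 2 gives the aim as "so as to choose a more effective and safe surgical method", and section 8.1 repeats this.

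**The concern.** When patients, physicians and equipment decide who has which operation, the groups can differ in features that drive the outcome. The SAP itself names two features tied to margins or to the feasibility of breast conservation: tumour extent (3.3.2, item 2) and breast volume (3.3.1, item 4). Item 5 of 3.3.1 also admits patients who become eligible after preoperative treatment, a further source of case-mix difference. Preoperative imaging is scheduled (3.1, 3.6), but no analysis uses it.

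Patient choice may also follow aesthetic demands, which bears directly on the cosmetic score.

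At stake is whether a difference in margin success, operation time, pain, cosmetic score or complications can be read as an effect of the operation. With the planned tests it cannot, yet sections 2 and 8.1 intend to read it that way.

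**Working it through.** **Inputs.** Group sizes are 20 versus 80 in the Scenario summary and 20 versus 60 in 4.1, so both are used. The SAP states no alpha, power, expected rates or effect size, so there is no planned figure to reproduce. Everything below is an illustration with assumed values: no true effect of the operation and a two-sided level of 0.05.

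**Continuous outcomes.** With the outcome in SD units, SE = √(1/n₁ + 1/n₂).

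- 20:60: √(1/20 + 1/60) = 0.258
- 20:80: √(1/20 + 1/80) = 0.250

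The false-positive rate is P(|Z + bias/SE| > 1.96).

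| Case-mix bias | 20:60 | 20:80 |
|---|---|---|
| 0.1 SD | 6.7% | 6.9% |
| 0.2 SD | 12.1% | 12.6% |
| 0.4 SD | 34.1% | 36.0% |

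A bias of 0.2 or 0.4 SD arises, for example, when a factor correlated 0.4 with the outcome differs by 0.5 or 1.0 SD between groups (0.4 × 0.5 = 0.2; 0.4 × 1.0 = 0.4).

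**Margin success.** Suppose a favourable factor is present in 80% of one group and 40% of the other.

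- Success 95% with it and 75% without: 0.8 × 95 + 0.2 × 75 = 91% versus 0.4 × 95 + 0.6 × 75 = 83%.
- Success 95% with it and 60% without: 0.8 × 95 + 0.2 × 60 = 88% versus 0.4 × 95 + 0.6 × 60 = 74%.

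Rejection rates by full enumeration of all possible tables:

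| Rates from case mix alone | Pearson, 20:60 / 20:80 | Fisher, 20:60 / 20:80 |
|---|---|---|
| 91% vs 83% | 8.2% / 9.1% | 5.6% / 6.3% |
| 88% vs 74% | 21.7% / 24.1% | 18.7% / 17.7% |
| 98% vs 96% | 0.7% / 2.2% | 0.2% / 0.4% |
| 97% vs 94% | 0.6% / 1.1% | 0.3% / 0.3% |
| 98% vs 93% | 0.3% / 0.4% | 0.1% / 0.1% |

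The binary test over-rejects only with a large imbalance in a strong factor. Near-perfect success, which the margin exclusion (3.3.2, item 4) and the conversion exit rule (3.3.3, item 1) could bring about, leaves a biased estimate but no excess of significant results.

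**Does adjustment help?**

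- *Linear adjustment* (8,000 simulated trials per case). With the confounder measured, bias falls to at most 0.004 SD and false positives to 4.8–5.2%. With only a proxy correlated 0.6, 0.13–0.14 of 0.2 SD remains, or 0.25–0.26 of 0.4 SD. With a proxy correlated 0.3, 0.18 of 0.2 SD remains, or 0.36 of 0.4 SD.
- *Firth logistic model for margin success, with a propensity score as covariate* (2,000 simulated trials per case, one measured factor, no true effect):

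| Expected total failures | Mean log odds ratio, crude | Adjusted |
|---|---|---|
| 18–23 | 0.91–0.94 | 0.00–0.02 in absolute value |
| 12–15 | 0.67 | −0.03 to −0.04 |
| 7–9 | 0.55–0.56 | −0.07 to −0.09 |
| 4–5 | 0.28–0.35 | −0.32 to −0.37 |

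A further simulation with five covariates behind the score and about 11–24 failures moved the log odds ratio from about 0.55 to between −0.01 and −0.07. With 4–5 failures adjustment fails.

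**The case against.** Five points can be made for the plan.

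1. **Eligibility already narrows case mix.** Tumour extent, breast volume, stage and age are filters applied to both groups. This makes large imbalances less likely, but shared criteria do not balance the groups within the eligible range.
2. **The stated drivers are not shown to be prognostic.** Nothing in the SAP links economic situation or equipment availability to margins, and equipment availability may be close to arbitrary. This stands: neither the existence nor the direction of bias is demonstrated. Physician advice and patient choice remain plausible routes, and the planned analysis could not detect or correct the bias.
3. **The larger figures need strong assumptions.** The 34–36% rests on a 1.0 SD imbalance, and 0.1 SD of bias gives under 7%. If the exact test is used whenever an expected count is below 5 (the SAP gives no rule), 91% versus 83% yields 5.6–6.3%, and 88% versus 74% yields 18.9–19.7%. This stands, and the size must be read as hypothetical.
4. **The study is early phase.** Section 4.3 is headed as preliminary, 4.1 defers the efficacy comparison to a later, larger sample, and the aim in section 2 is not a decision rule. Even so, 4.3 tests the primary endpoint between groups now.
5. **There are too few events to adjust.** This is true at about 95% success, where 4–5 failures are expected in 80–100 patients. It does not apply to pain, cosmetic score or operation time.

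The surgeon restriction in section 7, item 3, addresses skill, is worded for robotic patients and does not deal with patient selection.

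**Conclusion.** The concern holds. The unadjusted tests do not suit a comparison in which treatment is self-selected, and they cannot support a choice between operations. The estimate is biased whenever a prognostic factor is imbalanced. The risk of false significance is clear for continuous outcomes. For margin success it becomes material only with a large imbalance in a strong factor, and it disappears at very high success rates. The actual bias cannot be computed from the SAP, so all sizes rest on assumed imbalances, rates and level. The success rate of the robot group alone (3.8.1) is unaffected. The change should be made, but it does not undermine the study as a whole.

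**What to change.** Change 4.3 as follows.

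1. Pre-specify a short list of baseline confounders: age, clinical stage, tumour size or extent and breast volume where imaging yields them, and preoperative treatment if the CRF records it.
2. Report standardised differences between the groups.
3. Beside the unadjusted tests, report an adjusted estimate with a confidence interval. Use covariate adjustment or overlap weighting for continuous outcomes. For margin success, use a Firth logistic model with one summary score, only if there are about 10 or more failures in total. Otherwise give the two rates with exact intervals, descriptively; 19 of 20 successes, for instance, gives 75.1–99.9%.
4. In sections 2 and 8.1, limit the conclusion to an exploratory comparison and state that confounding by unrecorded factors, such as economic status and patient choice, remains.

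The cost is SAP wording and modest analysis work. Age, stage and imaging are covered by the schedule in 3.6, whereas tumour size, breast volume and preoperative treatment need a CRF check. Intervals for margin success widen somewhat: the SD of the log odds ratio rose from 0.73–0.75 to 0.83–0.89 in simulation. Only measured confounders are handled, and a weak proxy leaves most of the bias, so the adjusted result must not be presented as free of confounding.

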### 3.8 Endpoint evaluation index

To verify the safety and efficacy of the single-port robot (SPr) in breast conserving surgery, the primary endpoint of this study was the success rate of breast conserving surgery. Successful breast-conserving surgery was determined by a negative tumor margin at least 2-3mm from normal tissue, and secondary endpoints included postoperative pain score and cosmetic score.

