### 4. Statistical analysis plan

#### 4.1 Sample size estimation

This study belongs to the phase II clinical study, SPr-breast conserving surgery group enrolled 20 patients, and compared with the tradition-breast conserving surgery group (60 cases), aims to evaluate the single-port robot assisted axillary breast protection in the treatment of breast cancer, later further expand the sample size according to the situation, to compare the clinical efficacy of the two methods.

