#### 4.2 Statistical analysis of the population

This study, conducted only in the Army Characteristic Medical Center, is a single-center, prospective clinical cohort study designed to evaluate the safety and efficacy of single-port robots in breast cancer surgery by comparison with the traditional breast-conserving surgery group. During the trial, the clinical data will be

reviewed centrally to ensure uniform quality.

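### The primary endpoint gets only a test of difference and no interval estimate; with 20 robotic patients, a non-significant result could be misread as comparable efficacy

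*SAP*

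**What the plan says.** Section 3.8 states that "the primary endpoint of this study was the success rate of breast conserving surgery", with success defined by a negative margin. The whole primary analysis is one sentence in section 4.3: the success rate "will be compared by Chi-square test (Chi-square test) with exact test if necessary". The statistical paragraph of the Scenario summary likewise lists only tests. No effect measure, confidence interval, hypothesis, alpha, margin or performance threshold appears there, in sections 4.1 to 4.5, or elsewhere in the SAP.

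The aims are comparative. Section 4.2 describes the study as "designed to evaluate the safety and efficacy of single-port robots in breast cancer surgery by comparison with the traditional breast-conserving surgery group". Section 2 wants the comparison made "so as to choose a more effective and safe surgical method". Section 3.8 presents the primary endpoint as the means of verifying the technique.

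On size, section 4.1 says "SPr-breast conserving surgery group enrolled 20 patients", "compared with the tradition-breast conserving surgery group (60 cases"). The Scenario summary gives "Total number of cases: 100; 20 in the test group; 80 in the control group". The control numbers conflict. Section 4.1 also calls the study phase II and foresees a later enlargement for comparing clinical efficacy.

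**The concern.** Judging whether a new technique is good enough, or choosing between two techniques, requires knowing how much worse the new one could be. A p-value against no difference does not show this, and with 20 patients in one group it will often be non-significant even when a sizeable deficit is real. The group success rates will presumably be reported, since they are what is compared. What is missing is any planned statement of their uncertainty or of the uncertainty in their difference. Without it, a non-significant result could be misread as comparable efficacy, and a decision on enlarging the study would rest on two point estimates.

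**Working it through.** **Inputs from the SAP.** Robotic group n = 20 (section 4.1 and summary). Control group n = 60 (section 4.1) or 80 (summary); both are run. Section 4.1 gives no design inputs, so the stated sample size cannot be reproduced.

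**Assumptions.** Two-sided alpha 0.05, and the success rates shown below. None is in the SAP.

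**Step 1: power of Fisher's exact test.** Power is the sum of Bin(a; 20, p_R) × Bin(b; n_C, p_C) over all tables (a, b) whose two-sided Fisher p is below 0.05.

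| True success, robotic v control | Power, 20 v 60 | Power, 20 v 80 | Chance of a non-significant result |
|---|---|---|---|
| 80% v 90% | 19% | 22% | 78-81% |
| 85% v 95% | 27% | 30% | 70-73% |
| 75% v 95% | 64% | 69% | 31-36% |

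A true 10-point deficit is missed in roughly 70% to 81% of such studies. Even a 20-point deficit from 95% is missed in about a third.

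**Step 2: what identical observed rates leave open.** Take 19/20 v 76/80 (95% in each group; Fisher p = 1.00). The Wilson limits are [p + z²/2n ± z√(p(1−p)/n + z²/4n²)] / (1 + z²/n), with z = 1.96.

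- 19/20: (0.95 + 0.0960 ± 0.1355)/1.1921 = 0.7639 to 0.9911.
- 76/80: (0.95 + 0.0240 ± 0.0535)/1.0480 = 0.8784 to 0.9804.

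Newcombe's interval combines them around a difference of 0:

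- Lower: −√[(0.95 − 0.7639)² + (0.9804 − 0.95)²] = −√(0.03463 + 0.00092) = −0.189.
- Upper: +√[(0.9911 − 0.95)² + (0.95 − 0.8784)²] = +√(0.00169 + 0.00513) = +0.083.

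The 95% interval is -18.9 to +8.3 points. With 60 controls (19/20 v 57/60) it is -18.9 to +9.6. At 90% in each group (18/20 v 54/60) it is -20.8 to +12.5. The lower limit hardly changes between 60 and 80 controls because the 20 robotic patients dominate it.

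**Step 3: a non-significant observed deficit.** 17/20 v 57/60 is a difference of -10 points, with Fisher p = 0.16 and a Newcombe interval of -31.3 to +3.1 points.

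**Step 4: the robotic rate alone (Clopper-Pearson).** For 20/20 the lower 95% limit is 0.025^(1/20) = 83.2%. For 19/20 the interval is 75.1% to 99.9%.

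**Step 5: which test would apply.** The expected number of failures in the robotic group is 20 × (1 − overall success rate), which is below 5 whenever overall success exceeds 75%. Under the usual expected-count convention the exact test would therefore be used at any high success rate.

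**The case against.** The best defence is that this is a small phase II study and that section 4.1 looks to a later, larger sample for comparing clinical efficacy. That softens the point, because low power is less of a fault in an exploratory study. It does not remove it: sections 2, 3.8 and 4.2 still state comparative aims for this study, and exploratory work relies on estimates with intervals more than on tests. It is also fair that a reader given the rates and denominators could compute the interval. That is a reason to plan it, since it costs so little.

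Three stronger readings are tempting, and the SAP does not support them.

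- *That the plan treats non-significance as equality.* No section says so, and no equivalence or non-inferiority claim is made. The SAP leaves room for that misreading but does not prescribe it.
- *That the figures bear on safety.* The test concerns margin-based success. Complications are addressed separately in section 4.5 and fall under the general categorical tests in section 4.3. Nothing computed here speaks to them.
- *That the choice between chi-square and exact test could change the verdict.* For 16/20 v 57/60, uncorrected chi-square gives p = 0.040 and Fisher p = 0.062. But the smallest expected cell is 20 × 7/80 = 1.75, so the usual reading of section 4.3 already leads to the exact test. The SAP does not write the rule down, which is only a gap in wording.

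**Conclusion.** The point holds for efficacy on the primary endpoint. The SAP fixes a test of difference with no interval, and with 20 robotic patients that test cannot show whether the robotic success rate is close to the control rate. Under the assumed rates and two-sided 0.05, Fisher power is between 19% and 30% for a 10-point deficit and between 64% and 69% for 75% v 95%. Equal observed rates of 95% still leave a deficit of nearly 19 points inside the interval. The power figures move with the assumed rates, but the conclusion is the same for 60 or 80 controls. It should be corrected before analysis. It concerns how the result is reported and interpreted, and is no evidence that the technique performs worse.

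**What to change.** In section 4.3 and the Scenario summary, define the primary result as each group's success rate with an exact (Clopper-Pearson) 95% interval, together with the risk difference, robotic minus control, with a Newcombe 95% interval. Name Fisher's exact test as the accompanying test. Add that a non-significant test is not evidence of equivalence. Reconcile the control group size, 60 or 80, between section 4.1 and the summary.

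The cost is SAP wording and a few more numbers in one table. No extra patients, data or margin are needed. The price is a more modest conclusion.

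The SAP should also state the limit of this interval. Section 3.1 says "The choice of the two surgical methods is based on the patients economic situation and the availability of equipment", and section 3.4.1 adds physician advice and patient choice. An unadjusted interval therefore reflects sampling error only and does not correct for selection between the groups.

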### 3.3.3 Exit criteria

- 1) Those who cannot complete the single-port robot breast conserving surgery and need to be converted into traditional breast conserving surgery or endoscopic breast preservation surgery.
- 2) The patient voluntarily requests to withdraw from the investigator.
- 3) The patient is associated with other non-tumor conditions so that they cannot continue to accept the study program;
- 4) After inclusion in the study, the investigator cannot be completed due to other reasons.

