**3.6 Study process**

Experimental procedure	Enrollment-P reoperative	On the day of the operation	Postoperati ve hospital stay	follow-up period				
				28d	3m	6m	1y	3y
Basic data								
Informed consent	√							
Demographic data	√							
A history of tumor-related	√							
Check-up	√							
Vital sign	√							
Disease data								
Tumor stage	√		√					
Tumor molecular typing	√		√					
Immunohistochemistry of tumors	√		√					
Preoperative puncture	√		√					

biopsy								
laboratory examination								
Routine urine test	√							
Routine blood test	√			√	√	√	√	√
Blood biochemical	√			√	√	√	√	√
Coagulation function	√							
Electrocardiogram	√							
Echocardiogram	√							
Hepatitis B etiology caused by scientific examination	√							
Liver and kidney work	√			√	√	√	√	√
Blood fat	√			√	√	√	√	√
Color ultrasound (axillary lymph nodes, supraclavicular lymph nodes, breast)	√					√	√	√
Breast molybdenum target	√					√	√	√
Mammary gland MRI	√					√	√	√
Tumor marker								
CA-153	√			√	√	√	√	√
CA-199	√			√	√	√	√	√
CEA	√			√	√	√	√	√
Surgery-related indicators								
Operation time		√						
Intraoperative bleeding		√						
Dwelling time of the			√	√	√	√	√	√

drainage tube								
Length of stay			√	√	√	√	√	√
Post-operative pain score			√					
Postoperative beauty score				√	√	√	√	√

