#### 4.4 Effectiveness analysis

The primary endpoint of this study is the success rate of breast-conserving surgery in patients with breast cancer. The success of breast-conserving surgery was determined by a negative tumor margin at least 2-3mm from normal tissue. Secondary endpoints included surgical specimen quality, functional outcome, and quality of life (postoperative pain score, postoperative cosmetic score).

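### Converted robotic patients exit the study, no analysis set is defined and missing data are imputed without restriction, so the robotic success rate may rest on uncomplicated cases only

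*SAP*

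**What the plan says.** - **Missing data (4.3).** The whole rule is "Use multiple interpolation methods to deal with missing data". I read this as multiple imputation. No variables, model, assumption or sensitivity analysis is given, and the primary endpoint is not exempted.
- **Primary test (4.3).** "The success rate of breast conservation surgery under single hole robot will be compared by Chi-square test", with an exact test where needed.
- **Primary endpoint (3.8 and 4.4).** "The success of breast-conserving surgery was determined by a negative tumor margin at least 2-3mm from normal tissue". Section 3.8.1 and the Scenario summary name the endpoint more narrowly, as success under the single-port robotic approach.
- **Exit (3.3.3, criterion 1).** "Those who cannot complete the single-port robot breast conserving surgery and need to be converted into traditional breast conserving surgery", or into endoscopic surgery. The other three criteria are general; the second, for example, reads "The patient voluntarily requests to withdraw from the investigator".
- **Why patients convert (3.5, item 3).** Technical difficulty, an intraoperative complication or concern for patient safety.
- **Analysis population (4.2).** The heading is there, but the text describes only the setting and aim. It defines no analysis set.
- **Pathology.** Section 3.1 lists "postoperative pain score, and postoperative pathological biopsy" among the items recorded during the postoperative stay. Section 7, item 11, sends all patients' pathology to a core laboratory.
- **Conversion as an outcome.** The Scenario summary lists its incidence under surgical safety.
- **Cosmetic score (3.6).** "Postoperative beauty score" is scheduled at every follow-up visit from 28 days to 3 years. Section 3.1 follows mortality over the same period.

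**The concern.** Conversion happens in the operating theatre, before the final margin is reported. A patient who exits at that moment exits before the primary endpoint is known. Only robotic patients can exit this way, and they do so because the operation became difficult.

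The SAP does not say whether such a patient's margin is still used. If it is treated as missing, section 4.3 permits it to be imputed, and the lack of an analysis set equally permits the patient to be dropped. In both cases the robotic success rate comes from patients whose operation went to plan, while the control arm has no matching filter. With 20 robotic patients, one or two such cases visibly move the result.

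A smaller point concerns the cosmetic score. An unrestricted rule would also create scores for visits after a patient has died.

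**Working it through.** The SAP gives no expected success rate, conversion rate or power calculation, so there is no figure to reproduce. The counts below are assumptions chosen to show direction and scale.

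**Inputs.** Robotic arm n = 20 (Scenario summary and 4.1). Assumed: k converted patients whose margins are treated as missing, and f margin failures among the remaining 20 − k. Observed successes are s = 20 − k − f.

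**Formulas for the robotic success rate**

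- Dropped: s / (20 − k).
- Imputed from the arm's observed results, missing at random, with a Beta(s + 0.5, f + 0.5) posterior: expected value [s + k(s + 0.5)/(20 − k + 1)] / 20. For k = 4, f = 0: [16 + 4 × 16.5/17]/20 = 19.88/20 = 99.4%.
- All k truly margin failures: s / 20.

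| k | f | Dropped | Imputed | All k are failures | Imputed minus failures |
|---|---|---|---|---|---|
| 1 | 0 | 100% | 99.9% | 95% | 4.9 points |
| 2 | 0 | 100% | 99.7% | 90% | 9.7 |
| 3 | 0 | 100% | 99.6% | 85% | 14.6 |
| 4 | 0 | 100% | 99.4% | 80% | 19.4 |
| 1 | 1 | 94.7% | 94.6% | 90% | 4.6 |
| 2 | 1 | 94.4% | 94.2% | 85% | 9.2 |
| 3 | 1 | 94.1% | 93.8% | 80% | 13.8 |
| 4 | 1 | 93.8% | 93.2% | 75% | 18.2 |

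**Size per patient.** For dropping, the excess is s/(20 − k) − s/20 = (k/20) × s/(20 − k). That is at most k/20, or 5 points per lost failure. Imputation gives nearly the same.

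**Mixed case.** Suppose 3 patients convert, 2 of them with positive margins, and 16 of the 17 others are clear.

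- Truth: (16 + 1)/20 = 85.0%.
- Imputed at the observed proportion: (16 + 3 × 16/17)/20 = 18.82/20 = 94.1%.
- Dropped: 16/17 = 94.1%.

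The excess is 9.1 points either way. It comes from losing the observed margins, and the choice between imputing and dropping hardly matters.

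**If converted patients have clear margins.** With k = 4 and f = 1 the truth is 19/20 = 95.0%, against 93.8% dropped and 93.2% imputed. The error is then small (1.2 to 1.8 points) and goes against the robotic arm.

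**Effect on the comparison.** Assume 95% success in controls. With k = 4, all true failures, and f = 0, the robotic arm is really 80 − 95 = 15 points worse. It would appear 99.4 − 95 = 4.4 points better if imputed and 100 − 95 = 5 points better if dropped. On the true counts Fisher's exact test gives p = 0.062 with the 60 controls of section 4.1, and p = 0.049 with the 80 of the Scenario summary. That conflict in control numbers is a separate matter.

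**The case against.** The best reply is that the margin is never missing. Pathology is recorded after surgery for every patient, so a missing-data rule would not touch the primary endpoint. This is a fair reading and may be what the investigators intend. But the SAP does not say that the margin is used after exit, and exit comes before the pathology result. Nor would I lean on section 7 alone, since its core-laboratory text speaks of subcentres in a single-centre study. If the reply is right, the fix only writes it down.

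A reader might also infer more than the SAP supports:

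- **That the plan imputes exited patients.** It does not say so. Its rule allows it, and the missing analysis set equally allows dropping them.
- **That exits in general signal surgical failure.** Only criterion 1 concerns the operation. Voluntary withdrawal, non-tumour conditions and other reasons are not tied to failure.
- **That a converted patient has failed.** Sections 3.8 and 4.4 define success by the margin alone, and a converted patient may have a clear one. The narrower wording in 3.8.1 supports a sensitivity analysis, not a change to the primary definition.
- **That imputation itself causes the bias.** Dropping gives almost the same figures. Moreover, missing at random is conditional on the variables in the model, and the SAP names none. A conversion term would not rescue it, though: if every converted margin is treated as missing, no observed converted case remains to estimate that term.

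Exclusion criterion 4 (3.3.2), which removes patients whose margins cannot be cleared on re-resection, affects the success rate more directly. It is a separate point and does not answer this one.

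**Conclusion.** The point holds as a gap in the plan that should be closed before analysis. An exit that only robotic patients can meet, for reasons of surgical difficulty, combines with an undefined analysis set and an unrestricted imputation rule. Together they leave open whether converted patients' margins count.

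If they are lost, each true margin failure among them raises the robotic success rate by up to about 5 points. This assumes an arm of 20, that margins are treated as missing after exit, and that some converted patients have positive margins. The SAP gives no counts for any of this, so the size is illustrative; if converted patients have clear margins, the effect is small. The cosmetic-score issue is secondary, because the SAP gives no expected number of deaths.

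**What to change.** In sections 4.2 and 4.3, state that:

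1. every operated patient stays in the primary analysis, in the group of the planned operation;
2. the margin is taken from the pathology record regardless of exit or conversion, and is not imputed;
3. conversions are reported as the safety outcome named in the Scenario summary, with a sensitivity analysis of the primary endpoint that counts conversion as failure of the robotic approach (Scenario summary and 3.8.1);
4. multiple imputation is limited to missing pain and cosmetic scores, with its model stated;
5. no score is imputed after death, and the number of such patients is reported per arm.

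Exit criterion 1 should be reworded so that conversion does not end data collection, and exclusion criterion 4 must be reconciled with item 1.

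The cost is a few sentences and the use of records that the study already plans to hold. The robotic success rate may come out less favourable.
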